4.3.1.4. Appendix 3.1.4. Regulatory Considerations

This study will be conducted in accordance with the protocol and with the:

- consensus ethics principles derived from international ethics guidelines, including the Declaration of Helsinki and Council for International Organizations of Medical Sciences International Ethical Guidelines
- applicable ICH GCP Guidelines
- applicable laws and regulations

Some of the obligations of the Sponsor will be assigned to a third party.

4.3.1.5. Appendix 3.1.5. Investigator Information

Physicians with expertise in the diagnosis and treatment of alopecia areata will participate as investigators in this clinical trial.

4.3.1.6. Appendix 3.1.6. Protocol Signatures

The Sponsor's responsible medical officer will approve the protocol, confirming that, to the best of his/her knowledge, the protocol accurately describes the planned design and conduct of the study.

After reading the protocol, each principal investigator will sign the protocol signature page and send a copy of the signed page to a Lilly representative.

4.3.1.7. Appendix 3.1.7. Final Report Signature

Lilly will select a qualified investigator(s) from among investigators participating in the design, conduct, and/or analysis of the study to serve as the CSR coordinating investigator. If this investigator is unable to fulfill this function, another investigator will be chosen by Lilly to serve as the CSR coordinating investigator.

The CSR coordinating investigator will sign the final CSR for this study, indicating agreement that, to the best of his/her knowledge, the report accurately describes the conduct and results of the study.

The Sponsor's responsible medical officer and statistician will approve the final CSR for this study, confirming that, to the best of his/her knowledge, the report accurately describes the conduct and results of the study.

4.3.2. Appendix 3.2. Data Quality Assurance

To ensure accurate, complete, and reliable data, Lilly or its representatives will do the following:

- provide instructional material to the study sites, as appropriate.
- sponsor start-up training to instruct the investigators and study coordinators. This training will give instruction on the protocol, the completion of the CRFs, and study procedures.
- make periodic visits to the study site.

- be available for consultation and stay in contact with the study site personnel by mail, telephone, and/or fax.
- review and evaluate CRF data and use standard computer edits to detect errors in data collection.
- conduct a quality review of the database.

In addition, Lilly or its representatives will periodically check a sample of the patient data recorded against source documents at the study site. The study may be audited by Lilly or its representatives, and/or regulatory agencies at any time. Investigators will be given notice before an audit occurs.

The investigator will keep records of all original source data. This might include laboratory tests, medical records, and clinical notes. If requested, the investigator will provide the Sponsor, applicable regulatory agencies, and applicable ERBs with direct access to original source documents.

4.3.2.1. Appendix 3.2.1. Data Capture System

An electronic data capture system will be used in this study. The site maintains a separate source for the data entered by the site into the Sponsor-provided electronic data capture system.

ePRO measures (for example, a rating scale) and eCOAs are entered into an ePRO/eCOA instrument at the time that the information is obtained. In those instances where there is no prior written or electronic source data at the site, the ePRO/eCOA instrument record will serve as the source.

If ePRO/eCOA records are stored at a third-party site, investigator sites will have continuous access to the source documents during the study and will receive an archival copy at the end of the study for retention.

Any data for which the ePRO/eCOA instrument record will serve to collect source data will be identified and documented by each site in that site's study file.

CRF data will be encoded and stored in the electronic data capture system.

Data managed by a central vendor, such as laboratory test data, will be stored electronically in the central vendor's database system. Data will subsequently be transferred from the central vendor to the Lilly data warehouse.

Data from complaint forms submitted to Lilly will be encoded and stored in the global product complaint management system.

4.3.3. Appendix 3.3. Study and Site Closure

4.3.3.1. Appendix 3.3.1. Discontinuation of Study Sites

Study site participation may be discontinued if Lilly, the investigator, or the ERB of the study site judges it necessary for medical, safety, regulatory, or other reasons consistent with applicable laws, regulations, and GCP.

4.3.3.2. Appendix 3.3.2. Discontinuation of the Study

The study will be discontinued if Lilly judges it necessary for medical, safety, regulatory, or other reasons consistent with applicable laws, regulations, and GCP. Study termination may occur in a specific country or region when baricitinib is approved for the treatment of AA and becomes reimbursed or commercially available in that country or region, or a negative regulatory action or opinion is received in that country or region.

4.3.4. Appendix 3.4. Publication Policy

The publication policy for Study JAHO is described in the Clinical Trial Agreement.

4.4. Appendix 4. Hepatic Monitoring Tests for Treatment-Emergent Abnormality

Selected tests may be obtained in the event of a treatment-emergent hepatic abnormality and may be required in follow-up with patients in consultation with the Lilly, its designee, or the CRP.

Hepatic Monitoring Tests

Hepatic Hematology^a	Haptoglobin^a
Hemoglobin	
Hematocrit	Hepatic Coagulation^a
Erythrocyte count (RBC)	Prothrombin Time
Leukocytes (WBC)	Prothrombin Time, INR
Neutrophils, segmented	
Lymphocytes	Hepatic Serologies^{a,b}
Monocytes	Hepatitis A antibody, total
Eosinophils	Hepatitis A antibody, IgM
Basophils	Hepatitis B surface antigen
Platelets	Hepatitis B surface antibody
	Hepatitis B Core antibody
Hepatic Chemistry^a	Hepatitis C antibody
Total bilirubin	Hepatitis E antibody, IgG
Direct bilirubin	Hepatitis E antibody, IgM
Alkaline phosphatase	
ALT	Anti-nuclear antibody^a
AST	
GGT	Alkaline Phosphatase Isoenzymes^a
CPK	
	Anti-smooth muscle antibody (or anti-actin antibody)^a

Abbreviations: ALT = alanine aminotransferase; AST = aspartate aminotransferase; CPK = creatinine phosphokinase; GGT = gamma-glutamyl transferase; Ig = immunoglobulin; INR = international normalized ratio; RBC = red blood cell; WBC = white blood cell.

^a Assayed by Lilly-designated or local laboratory.

^b Reflex/confirmation dependent on regulatory requirements and/or testing availability.

4.5. Appendix 5. Liver Function Testing and Hepatic Safety Monitoring

Liver Function Testing and Hepatic Safety Monitoring

Analyte	Exclusion Criteria	Additional Hepatic Testing	Hepatic eCRF Reporting	Temporary Interruption of IP	Permanent Discontinuation of IP after Consultation with the Lilly-Designated Medical Monitor
Protocol Section	Section 6.2	Section 9.4.10.1	Section 9.4.10.1	Section 8.1.1	Section 8.1.1
ALT/AST	$\geq 2 \times \text{ULN}$	As per protocol only ALT $> 3 \times \text{ULN}$	As per protocol only ALT $\geq 5 \times \text{ULN}$ on ≥ 2 consecutive tests	$\geq 5 \times \text{ULN}$	
 $> 8 \times \text{ULN}$ $> 5 \times \text{ULN}$ for > 2 weeks $> 3 \times \text{ULN}$ AND TBL $> 2 \times \text{ULN}$ or INR > 1.5 $> 3 \times \text{ULN}$ with symptoms^a
ALP	$\geq 2 \times \text{ULN}$	$\geq 2 \times \text{ULN}$	$\geq 2 \times \text{ULN}$ on ≥ 2 consecutive tests	No applicable criteria	
 $> 3 \times \text{ULN}$ $> 2.5 \times \text{ULN}$ AND TBL $> 2 \times \text{ULN}$ $> 2.5 \times \text{ULN}$ with symptoms^a
TBL	$\geq 1.5 \times \text{ULN}$	$\geq 2 \times \text{ULN}$	$\geq 2 \times \text{ULN}$ (excluding Gilbert's syndrome)	No applicable criteria	
 ALT or AST (as per protocol) $> 3 \times \text{ULN}$ AND TBL $> 2 \times \text{ULN}$ ALP $> 2.5 \times \text{ULN}$ AND TBL $> 2 \times \text{ULN}$

Abbreviations: ALP = alkaline phosphatase; ALT = alanine aminotransferase; AST = aspartate aminotransferase; eCRF = electronic case report form; INR = international normalized ratio; IP = investigational product; TBL = total bilirubin level; ULN = upper level of normal.

^a Fatigue, nausea, vomiting, right upper-quadrant pain or tenderness, fever, rash, and/or eosinophilia ($> 5\%$).

4.6. Appendix 6. Provisions for Changes in Study Conduct During Exceptional Circumstances

Implementation of this appendix

The changes to procedures described in this appendix are temporary measures intended to be used only during specific time periods as directed by the sponsor in partnership with the investigator.

Exceptional circumstances

Exceptional circumstances are rare events that may cause disruptions to the conduct of the study. Examples include pandemics or natural disasters. These disruptions may limit the ability of the investigators, participants, or both to attend on-site visits or to conduct planned study procedures.

Implementing changes under exceptional circumstances

In an exceptional circumstance, after receiving the sponsor's written approval, sites may implement changes if permitted by local regulations.

After approval by local ERBs, regulatory bodies and any other relevant local authorities, the implementation of these exceptional circumstances changes will not typically require additional notification to these groups, unless they have specific conditions in which notification is required. To protect the safety of study participants, urgent changes may be implemented before approval but need to be reported as soon as possible. All approvals must be retained in the study records.

In the event written approval is granted by the sponsor for changes in study conduct, additional written guidance, if needed, will be provided by the sponsor.

Considerations for making a change

The prevailing consideration for making a change is ensuring the safety of study participants. Additional important considerations for making a change are compliance with Good Clinical Practice, enabling participants to continue safely in the study and maintaining the integrity of the study.

Informed Consent

The site should document the participant's verbal consent for having remote visits and remote dispensing of IP, ancillaries, prior to the implementation of these activities.

Additional consent from the participant will be obtained, if required, for:

- participation in remote visits, as defined in Section "Remote Visits"
- a change in the method, location, or both, of study intervention administration
- dispensation of additional study intervention during an extended treatment period
- alternate delivery of study intervention and ancillary supplies, and
- provision of their personal or medical information required prior to implementation of these activities.

Changes in Study Conduct During Exceptional circumstances

Changes in study conduct not described in this appendix, or not consistent with applicable local regulations, are not allowed.

The following changes in study conduct will not be considered protocol deviations.

1. Remote visits

Visit 11 (Week 52) requires a live clinical assessment because it is the primary outcome visit. To facilitate an onsite visit, the visit window may be extended (see below in Adjustment to Visit Windows of this appendix).

All other visits may be conducted remotely if the visit could not otherwise be conducted due to local or national restrictions.

In source documents and the CRF, the study site should capture the visit location and method, with a specific explanation for any data missing because of missed in-person site visits.

Telemedicine: Live, onsite clinical efficacy assessments are preferred for ALL visits. However, if a remote visit is the only option, telephone or technology-assisted virtual visits, or both, are acceptable to complete appropriate assessments (with the exception of Visit 11). Assessments to be completed in this manner include:

- PRO Scalp, SALT Score, and ClinROs for Eyebrows/Eyelashes if Visual Assessment by telemedicine is possible. If NO visual assessment AND ONLY verbal assessment by phone is possible. SALT, ClinROs for Eyelash/Eyelash should not be assessed.
- AEs and product complaints
- concomitant medications
- C-SSRS (Since Last Visit Version)
- Photos should be captured at next onsite visit after a remote V8 or V11/ET

Regardless of the type of remote visits implemented, the protocol requirements regarding the reporting of AEs, SAEs, and product complaints remain unchanged. Furthermore, every effort should be made to enable participants to return to on-site visits as soon as reasonably possible, while ensuring the safety of both the participants and the site staff.

2. Local laboratory testing option

Local laboratory testing may be conducted in lieu of central laboratory testing. The local laboratory must be qualified in accordance with applicable local regulations.

- Obtain local labs for safety (hematology, chemistry) and urine pregnancy when applicable, as per the study protocol schedule of activities.
- A urine pregnancy test should be sent to female patients of child bearing potential. The patient should conduct the test and provide the verification of results to the site per a method agreed to between the patient and the site. Investigational product must be temporarily held until site can review photo of pregnancy test results.

- All labs will be reviewed by the investigators. Lilly Medical should be informed of any labs that meet criteria for temporary or permanent study drug discontinuation.
- Sign and date review of local labs per normal process and follow-up with the patient as needed. Results will not be recorded in the eCRF.
- Safety labs should be obtained at a minimum of every 12 weeks and IP should not be dispensed until these can be collected and reviewed.

3. Study intervention and ancillary supplies

When a participant is unable to go to the site to receive study supplies during normal on-site visits, the site should work with the sponsor to determine appropriate actions. These actions may include:

- asking the participant to go to the site and receive study supplies from site staff without completion of a full study visit
- asking the participant's designee to go to the site and receive study supplies on a participant's behalf, and
- arranging delivery of study supplies.

These requirements must be met before action is taken:

- Sponsor approves the alternative method of delivery, taking local regulatory requirements into consideration.
- Participant consents verbally to alternate method of delivery.
- Site confirms the participant's receipt of the trial supplies.
- Site/sponsor confirms appropriate ethics review board notification.
- Alternate delivery of IP should be performed in a manner that does not compromise treatment blinding and ensures product integrity. The existing protocol requirements for product accountability remain unchanged, including the verification of participant's receipt of study supplies.
- When delivering supplies to a location other than the study site (for example, participant's home), the investigator, sponsor, or both should ensure oversight of the shipping process to ensure accountability and product quality (that is, storage conditions maintained and intact packaging upon receipt).
- Instructions may be provided to the participant or designee on the final disposition of any unused or completed study supplies.

4. Screening period guidance

Not Applicable

5. Adjustments to visit windows

Whenever possible and safe to do so, as determined by the investigator's discretion, participants should complete the usual Schedule of Activities. To maximize the possibility that these visits can be conducted as on-site visits, the windows for visits may be adjusted,

upon further guidance from the sponsor. This minimizes missing data and preserves the intended conduct of the study.

This table describes the allowed adjustments to visit windows.

Visit Number	Tolerance
Visits 11	Visits 11 (Week 52) may be conducted within 7 days before the intended date, or up to 28 days after the intended date
All other Visits	All other visits should be conducted as per the visit window the stated in the Schedule of Activities in Section 2.2

Documentation

Changes to study conduct will be documented:

- Sites will identify and document the details of how participants, visit types, and conducted activities were affected by exceptional circumstances.
Dispensing/shipment records of study intervention and relevant communications, including delegation, should be filed with site study records.
- Source documents generated at a location other than the study site should be part of the investigator's source documentation and should be transferred to the site in a secure and timely manner.

Signature Page for VV-CLIN-074217 v3.0

Approval	PPD 14-Mar-2024 15:17:39 GMT+0000
----------	--------------------------------------

Approval	PPD 14-Mar-2024 15:23:11 GMT+0000
----------	--------------------------------------

Signature Page for VV-CLIN-074217 v3.0

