2.6.8. Treatment after the End of the Study**2.6.8.1. Continued Access**

After the conclusion of the study, continued access to baricitinib will not be provided. Patients will be referred to their local treatment centers for AA therapy, as clinically indicated.

2.7. Discontinuation Criteria**2.7.1. Discontinuation from Study Treatment****2.7.1.1. Permanent Discontinuation from Investigational Product**

IP should be permanently discontinued if the patient or the patient's designee requests to discontinue IP.

Discontinuation of the IP for abnormal liver tests should be considered by the investigator when a patient meets 1 of the following conditions after consultation with the Lilly-designated medical monitor:

- ALT or AST $>8 \times$ ULN
- ALT or AST $>5 \times$ ULN for more than 2 weeks
- ALT or AST $>3 \times$ ULN and TBL $>2 \times$ ULN or international normalized ratio >1.5
- ALT or AST $>3 \times$ ULN with the appearance of fatigue, nausea, vomiting, right upper-quadrant pain or tenderness, fever, rash, and/or eosinophilia ($>5\%$)
- ALP $>3 \times$ ULN
- ALP $>2.5 \times$ ULN and TBL $>2 \times$ ULN
- ALP $>2.5 \times$ ULN with the appearance of fatigue, nausea, vomiting, right quadrant pain or tenderness, fever, rash, and/or eosinophilia ($>5\%$)

NOTE: Patients who are discontinued from IP due to a hepatic event or liver test abnormality should have additional hepatic safety data collected via the hepatic safety eCRF.

IP should be permanently discontinued if any of the following are observed:

- white blood cell count <1000 cells/ μL ($1.00 \times 10^3/\mu\text{L}$ or 1.00 GI/L)
- absolute neutrophil count <500 cells/ μL ($0.50 \times 10^3/\mu\text{L}$ or 0.50 GI/L)
- lymphocyte count <200 cells/ μL ($0.20 \times 10^3/\mu\text{L}$ or 0.20 GI/L), and
- hemoglobin <6.5 g/dL (<65.0 g/L).

NOTE: Temporary interruption rules (see Section 2.7.1.2) must be followed, where applicable. For laboratory values that meet permanent discontinuation thresholds, IP should be discontinued. However, if, in the opinion of the investigator, the laboratory abnormality is due to intercurrent illness, such as cholelithiasis or another identified factor, laboratory tests may be repeated. Only when the laboratory value meets resumption thresholds (Table JAHO.2) following the resolution of the intercurrent illness or other identified factor, may the investigator restart IP, after consultation with the Lilly-designated medical monitor.

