2.9.5. Safety Analyses

All safety data will be descriptively summarized and analyzed using the safety population unless, otherwise, stated.

Treatment-emergent adverse events are defined as AEs that first occurred or worsened in severity after the first dose of study treatment. The number of TEAEs, as well as the number and percentage of patients who experienced at least 1 TEAE, will be summarized using the Medical Dictionary for Regulatory Activities for each system organ class (or a body system) and each

preferred term. Serious adverse events and AEs that lead to discontinuation of IP will also be summarized.

All clinical laboratory results will be descriptively summarized. Individual results that are outside of normal reference ranges will be flagged in data listings. Quantitative clinical hematology, chemistry, and urinalysis variables obtained at the Baseline to postbaseline visits will be summarized as changes from Baseline. Categorical variables, including the incidence of abnormal values and incidence of AEs of special interest, will be summarized by frequency and percentage of patients in corresponding categories. Shift tables will be presented for selected measures.

Observed values and changes from Baseline for vital signs and physical characteristics will be descriptively summarized by timepoint. Change from Baseline in vital signs and body weight will be descriptively summarized.

Summary tables or listings for the C-SSRS will be produced, as needed.

The incidence and average duration of IP interruptions will be summarized descriptively (if necessary). Further analyses may be performed and will be planned in the SAP.

Full details of the safety analyses and any derivations of AEs of special interest will be documented in the program safety analysis plan and study SAP, if needed.

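### Local laboratory results that replace central tests have no stated route into the laboratory dataset, so the laboratory tables and listings can omit out-of-range values

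*Protocol*

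**What the plan says.** Appendix 6 of the protocol (Section 4.6) sets out "temporary measures intended to be used only during specific time periods as directed by the sponsor", working with the investigator. Within it, item 2 says: "Local laboratory testing may be conducted in lieu of central laboratory testing". This covers safety hematology and chemistry, and urine pregnancy tests. The investigator reviews, signs and dates the local reports. On data capture the instruction is: "Results will not be recorded in the eCRF". For serious values it adds: "Lilly Medical should be informed of any labs that meet criteria for temporary or permanent study drug discontinuation". No dataset is named for that notice.

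Appendix 3.2.1 describes how laboratory data normally arrive: "Data managed by a central vendor, such as laboratory test data, will be stored electronically in the central vendor's database system". From there they pass to the sponsor's data warehouse.

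Section 2.9.5 sets the reporting commitment: "All clinical laboratory results will be descriptively summarized", and "Individual results that are outside of normal reference ranges will be flagged in data listings". It also plans changes from baseline, the incidence of abnormal values, and shift tables for selected measures.

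**The concern.** The local results are real safety data. Appendix 6 makes further dispensing depend on their collection and review, and it foresees that some will meet hold or stop criteria. Section 2.7.1.1 says "IP should be permanently discontinued if any of the following are observed" and lists white cell, neutrophil, lymphocyte and hemoglobin limits. Table JAHO.2 gives hold limits for those measures and for platelets, eGFR and ALT/AST. A value that decides whether a patient stays on drug can therefore be obtained, reviewed and acted on, yet never reach the tables meant to describe laboratory safety.

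At stake is whether a reader of the laboratory outputs can rely on them as complete. In a group of 20 a single event is visible, so one omission changes what a row says.

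**Working it through.** There is no plan figure to reproduce, because the addendum has no power calculation and this is a question of data flow. The check has two parts.

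**Part 1: follow a local value through the documents.**

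- *Central-vendor transfer (Appendix 3.2.1):* bypassed, because the local test is done instead of the central one.
- *eCRF (Appendix 6, item 2):* closed by instruction.
- *Notice to the sponsor's medical staff (Appendix 6, item 2):* covers only values that meet a hold or stop criterion, and is not described as feeding a dataset.
- *Adverse event record (Section 2.8.2; Appendix 1):* open. Appendix 6 leaves AE and SAE reporting unchanged, and the AE definition can cover an abnormal laboratory finding. It records an event, not a value that a shift or change-from-baseline table can use.
- *Discontinuation and interruption records:* Section 2.9.5 summarizes AEs leading to discontinuation and, if necessary, interruptions. SAP 4.14.2.3 lists all interruptions with reasons. These also carry no laboratory value.
- *Hepatic safety eCRF (Section 2.7.1.1, Appendix 5):* open for specified liver-test findings. It does not cover hematology cell counts below their limits, or eGFR.
- *CRF note explaining data missing after missed in-person visits (Appendix 6, item 1):* records why a value is absent, not the value.

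So no stated route brings the number into the laboratory dataset. Out-of-range values below a hold or stop criterion have no route at all unless the investigator records an AE. SAP 4.2.2 would accept such values if they were captured: apart from continuous by-visit analyses, its safety analyses use every non-missing measurement after the first dose.

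**Part 2: size.**

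Inputs from the protocol: 20 patients (Section 2.4.2), and hematology and chemistry at 9 post-baseline treatment visits, Weeks 4, 8, 12, 16, 24, 36, 40, 44 and 52 (Section 2.2). Week 52 must be a live visit (Appendix 6, item 1).

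- Ceiling on exposure, taking Week 52 as central: 8 of 9 visits, or 20 × 8 = 160 of 20 × 9 = 180 patient-visits. This is an extreme, not an expectation.
- One omitted abnormality: 1/20 = 5 percentage points.
- For scale, the Wilson 95% interval without continuity correction (the protocol names it for efficacy proportions; it is used here only as an illustration): [p + z²/2n ± z√(p(1−p)/n + z²/4n²)] / (1 + z²/n), with n = 20 and z = 1.96. This gives 0/20 = 0% (0 to 16.1%), 1/20 = 5% (0.9 to 23.6%) and 2/20 = 10% (2.8 to 30.1%).
- Effect of omitted normal results: if a patient with only normal local results drops out of an observed-case denominator, 1/20 = 5.0% becomes 1/19 = 5.3%.

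The chance that at least one threshold event is seen only on a local draw is 1 − (1 − rs)^20. Here r is the per-patient risk of such an event and s is the share of draws that are local. Neither is in the documents; both are assumptions.

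| r | s = 10% | s = 50% |
|---|---|---|
| 2% | 3.9% | 18.2% |
| 5% | 9.5% | 39.7% |
| 10% | 18.2% | 64.2% |

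The formula treats each event as seen on one draw, independently of whether that draw is local.

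**The case against.** The best defence is that the commitment in Section 2.9.5 concerns the central dataset. Appendix 2 says the protocol panels are assayed by the sponsor-designated laboratory, and Appendix 3.2.1 describes only central transfer. On that reading, leaving out local values avoids mixing assays and reference ranges. This stands for continuous by-visit summaries. It does not settle the categorical tables and listings, because neither document states that local values are excluded, and Section 2.9.5 contains no such limit.

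It is also fair that the provision is exceptional, temporary and subject to the sponsor's written approval. Appendix 6 allows for further written guidance, and the SAP defers laboratory detail to separate compound-level safety standards. Either could hold a rule on local values; neither is available here.

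A reader might infer more than the documents support:

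- *That values which stop or hold treatment vanish from the safety tables altogether.* They do not. The AE, interruption and discontinuation outputs remain, and liver findings have their own form.
- *That such values exist only in site files and cannot be traced.* Those meeting a hold or stop criterion are notified to the sponsor's medical staff, and source records are open to the sponsor on request (Appendix 3.2).
- *That a patient tested only locally is counted as normal.* No text says a missing laboratory value counts as normal. The laboratory denominator is not specified, so the patient might instead drop out of the row.
- *That the error runs only downward.* This is true of raw abnormality counts, but percentages can rise if denominators shrink, and by-visit means can move either way.

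**Conclusion.** The point holds as a gap in the laboratory data, limited to laboratory values, tables and listings. Appendix 6 item 2 and Section 2.9.5 cannot both be followed as written once the local option is used. Hematology, eGFR and out-of-range values below the hold or stop criteria are the least protected.

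Each omitted abnormality is worth 5 percentage points when the denominator is 20. Whether any was omitted cannot be judged, since the documents do not report use of the option; if it was never used, the effect is nil. The probabilities in the table rest wholly on assumed event risks and local shares, and show only that the loss of one event is plausible under moderate use. This merits correction because the remedy is small, not because harm to the results has been shown.

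**What to change.** Replace the data-capture sentence in Appendix 6, item 2, so that local results taken in place of central tests are entered in the eCRF with value, unit, reference range and date. At a minimum, enter every out-of-range result and every result that meets an existing interruption or discontinuation threshold. In the SAP:

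- include local values in the categorical (treatment-emergent and shift) summaries;
- mark them as local in the listings;
- keep them out of the continuous by-visit summaries;
- report the number of patient-visits that relied on local tests.

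The values should be recoverable, since the investigator signs each local report and off-site source documents are transferred to the site. The cost is a short local-laboratory form, a little site data entry, and mixed reference ranges in the categorical tables. Enrollment is complete, so the form would be added after the fact. If that is judged impracticable, the lesser remedy is to limit Section 2.9.5 to central results and state the exclusion in the clinical study report with the count of affected patient-visits. This reconciles the text but does not recover the values. Neither option changes a clinical threshold or management rule.
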